7.4.2.4 Fecal calprotectin

Fecal calprotectin is a calcium and zinc binding protein with a molecular weight of 36,000 Daltons. It is derived from neutrophils and accounts for 60% of the cytoplasmic proteins in granulocytes. Fecal calprotectin is confirmed to be a measure of the migration of neutrophils into the gastrointestinal tract. Fecal calprotectin is a very stable marker (stable for 1 week at

room temperature).

Fecal calprotectin testing will be completed by the central laboratory at screening, week 12, week 24 (only for sub-study 2 of the study stage 2) and week 48.

7.5. Monitoring of adverse events of special interest

During the study on CBP-307, AEs caused by S1P1 receptor stimulation that were found in previous clinical studies on other similar drugs will be closely monitored. These AEs include:

- a. Bradycardia and cardiac conduction abnormalities: It was reported that the adverse reactions caused by the first dose of similar drugs mainly included reversible bradycardia, first grade atrioventricular block and sinus arrest. Reduced heart rate is an expected adverse reaction to S1P1 agonists. These negative chronotropic effects of S1P1R agonists appear to attenuate over time after S1PR desensitization and internalization into cardiac myocytes. This effect appears to occur with increasing exposure to study drug; thus, gradual titration of the dose of CBP-307 within 1 week may mitigate against larger reductions in heart rate.
- b. Pulmonary toxicity: An initial sharp decrease followed by slow progressive decline over time in FEV₁ was observed in clinical studies of the same category of drugs. In this study, FEV₁ and FVC in all subjects will be measured; DLCO will be measured in sites that are equipped with the right facilities. Each subject with abnormal pulmonary function test results will be followed up. If the subject's pulmonary function test results (FEV₁ and/or FVC) fall below 50% of the predicted values, treatment should be discontinued immediately, and appropriate clinical follow-up (for at least 3 months) should be performed until the resolution is confirmed or no further aggravation is expected by investigator.
- c. Hepatotoxicity: fingolimod caused frequent, reversible liver enzyme elevations greater than 3-fold above the ULN in up to 12% of patients. In the completed phase I clinical study on CBP-307, ALT levels slightly increased in individual subjects but were all below 3 times the ULN; and this side effect was also milder than that of fingolimod. In this study, blood chemistry analysis will include measurement of LFT levels. Subjects with abnormal LFT levels will be continuously followed up until the LFT values returns to the normal/baseline level.
- d. Macular edema: In the preclinical and clinical phase I studies of CBP-307, no eye-related toxicity was observed yet. In this trial, OCT examination will be included. Subjects with macular edema must discontinue the investigational product and undergo examinations including a dilated fundus examination. Every subject whose ophthalmic evaluations reveal abnormalities will be followed until values return to baseline.
- e. Opportunistic infection or severe infection: Tuberculosis, serious bacterial infections, systemic fungal infections, viral infections such as herpes infections (including herpes

- zoster and disseminated herpes simplex) and protozoal infections during the study should be reported as AESI.
- f. Basal cell carcinoma: In a 2-year placebo-controlled clinical study on fingolimod (a similar drug), the incidences of basal cell carcinoma are 2.0% in the group treated with fingolimod 0.5 mg and 0.1% in the placebo control group, respectively. Subjects should be observed for suspected skin lesions, and a specialist assessment should be performed immediately if any suspected skin lesions are noted.
- g. Posterior reversible encephalopathy syndrome and progressive multifocal leukoencephalopathy.

The following steps should be followed:

- a. At every visit, vital signs should be measured in the supine position.
- b. Subjects will be closely monitored in the clinic after their first dose of the initial dose titration regimen for a period of 6 hours after administration. ECGs will be performed predose and at 4 and 6 hours after drug administration, with more frequent assessments as clinically indicated. Vital signs will be measured before administration and at every hour in 6 hours after administration. During titration period, continuous overnight cardiac monitoring should be performed in patients who experience symptomatic bradycardia that requires pharmacologic intervention. In these patients, the first-dose monitoring strategy will continue the following days until the symptoms improve by investigator's assessment, even if the study drug is discontinued. If anyone has prolonged QTc interval during 6-hour observation after dosing, repeated cardiac monitoring in the following days will be conducted until the abnormity improves.
- c. Prior to drug administration in the clinical study, clinicians should pay attention to subjects with a lower heart rate (occurring spontaneously or being induced by β-blockers) at baseline. Atropine IV is recommended as the first line therapy for bradycardia, with a daily maximum dose of 3 mg. Furthermore, the common guidelines for treatment of bradycardia (e.g., Advanced Cardiac Life Support-ACLS guidelines) should be followed as appropriate:).
 - In case of clinical symptoms or hypotension, give subjects atropine 1 mg and repeated doses within 3-5 minutes.
 - If the heart rate and/or blood pressure remain unresponsive, consider administration of dopamine drip 5-20 μg/kg/min or epinephrine drip 2-10 μg/min can be given.
 - Performance Transcutaneous pacing can also be considered.
 - In the condition of decreased blood pressure, isoproterenol should be avoided or used with caution.
- d. If there is any condition that may affect the pulmonary function test results (FEV₁, FVC, and DLCO), including infections, respiratory symptoms, occupational exposure (including asbestos) and smoking, it is required to collect information and document it in

the eCRF before each pulmonary function test. If the subject's pulmonary function test results (FEV₁ and/or FVC) fall below 50% of the predicted values, the investigational product treatment should be discontinued. If a subject discontinues due to respiratory AE, the investigator should ensure that the subject has adequate evaluations as clinically indicated by a pulmonologist (consider PFTs, chest X-ray or high-resolution computed tomography, based on findings of the other examinations) at the time of the AE. For subjects with pulmonary nodules, lung biopsy should be taken into account. Follow up the subject (for at least 3 months) until a resolution is confirmed or no further aggravation or improvement is expected by investigators.

- e. If the subject's LFT (ALT or/and AST) is elevated and greater than 3 times the ULN, a retest should be performed within a week. Upon confirmation of the abnormality, retests should be performed weekly until the elevated LFT decreases below 3 times the ULN. If the LFTs increase is confirmed to be above 5 times the ULN the study drug must be permanently discontinued.
- f. All subjects diagnosed with macular edema must discontinue the investigational product. Based on the judgment by the ophthalmologist, follow up subjects with macular edema monthly or more frequently if needed. Follow up the subject (for at least 3 months) until a resolution is confirmed or no further aggravation or improvement is expected by investigators. If the subject does not show definite signs of improvement on examination 6 to 8 weeks after discontinuation of study drug, then therapy for macular edema in conjunction with an ophthalmologist experienced in the management of this condition should be initiated.
- g. Examination of the skin for lesions will be performed as part of the physical examination at screening and at the end of study. If skin lesions are noted, the subject will be referred to a dermatologist for evaluation and follow-up care.
- h. Nervous system physical examinations are required for each visit, and the investigators should actively query about nervous system symptoms such as cephalgia, convulsions, confusion, vision loss, speech disturbances, facial drooping, weakness, problems with coordination, gait and sensory loss, and mental impairment. If any of the above symptoms appears, a neurology consult would be ordered for further assessment, and extra examinations including CT scanning, MRI examination and other related tests will be conducted by neurologists' judgment.

8 DEFINITION, MONITORING AND REPORTING OF A SAFETY EVENT

All AEs will be managed and reported in accordance with applicable regulations. If an AE occurs, the first thing that needs attention is the safety of the subject. If necessary, the subject needs to be treated accordingly. AEs will be summarized in the final clinical study report.

The informed consent form signed by the subject should include the name of the investigator

and the contacts used to report AEs and medical emergencies.

8.1. Adverse event

8.1.1. Definition and recording of adverse events

Definition: An adverse event refers to any untoward medical occurrence that occurs after the subjects signs the ICF, which does not necessarily have a causal relationship with the investigational product. Thus, an AE can be any unfavorable and unintended symptom, sign, disease or condition, or an abnormal test finding, whether or not it is related to the investigational product. AEs include:

- Symptoms described by the subject, or signs observed by the investigator, and
- Abnormal findings (involving laboratory tests, ECG, and an X-ray) that result in changes in medical care (diagnostic or therapeutic).
- Exacerbation of chronic or intermittent pre-existing diseases, including increased incidence and/or diseases severity.

An abnormality found at screening visit is not an AE unless it has reappeared after disappearance or is worsened during the trial.

Note: Regarding a heart rate decrease (bradycardia) and decreased lymphocyte count in peripheral blood in this study, please report them as follows:

- Since a decreased lymphocyte count in peripheral blood is due to the mechanism of action of the drug, it itself is not to be reported as an AE. However, clinical diagnosis related to a decreased lymphocyte count in peripheral blood indicates AE reporting (if no diagnosis is available, it is required to report related clinical symptoms or signs).
- The heart rate decrease (bradycardia) in this study is defined as a heart rate of <50 beats per minute in the awake state or a heart rate of ≥50 beats per minute in the awake state whereas subjects experience clinical symptoms due to a reduced heart rate (if subjects have a heart rate <50 beats per minute in the awake state and need clinical treatment, such condition is considered a grade II AE).

In this study, AE data will be collected after subjects sign informed consent forms, and AEs will be persistently monitored throughout the study, i.e., until 28 days after the last dose.

The investigator will ask the subject at each follow-up visit if any AE has occurred since the last visit. All AEs will be recorded in medical records and eCRFs, including the AE terms, severity of AEs, the start date and time of occurrence, the stop date and time of occurrence, seriousness (i.e., whether it is a SAE), CTCAE grade, the relationship to the investigational product, actions taken on the investigational product, medications/treatments given, and outcomes of AEs. Once a written ICF is signed by the subject, the investigator will start recording the AE until 4 weeks after the last dose.

Outcome of an AE:

- Death: end of life as the result of the AE.
- Unrecovered/unresolved: subjects fail to recover, or an AE is not improved.
- Recovering/resolving: subjects are recovering, or an AE is improving.
- Recovered/resolved: subject has recovered or an AE has been resolved.
- Recovered/resolved with a sequela: an AE has been resolved, but subjects have been left with symptoms or pathological manifestations.
- Unknown: no detail, not observed, not recorded, or refusal to provide relevant information.

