8.1.2. Grading of adverse events

All AEs in the trial will be graded according to the Common Terminology Criteria for Adverse Events (CTCAE), version 5.0. NCI CTCAE is originally a standard term designed to report AEs that occur during cancer clinical trials. CTCAE contains a grading scale representing the severity of an event, from grade 1 to grade 5.

- Grade 1: mild; asymptomatic or mild symptoms; clinically or diagnostically observed; no intervention required.
- Grade 2: moderate; indicating minimal local non-invasive intervention; instrumental activity of daily living corresponding to age is restricted (applicable to AEs involving metabolism, nutrition and immunity).
- Grade 3: a severe or medically important event, but not immediately life-threatening; resulting in hospitalization or prolonged hospital stay; disability; restriction of self-care activity of daily living.
- Grade 4: a life-threatening consequence; indicating emergency treatment.
- Grade 5: deaths related to AE.

Note: The CTCAE provides specific grading scales for abnormalities shown in a laboratory test. Grade 4 abnormality shown by a laboratory test does not automatically represent a life-threatening event. An abnormal result shown by a laboratory test still needs to be evaluated before it is determined whether such result is an AE or not.

The safety data from the ongoing trial will be submitted to the medical monitor for review.

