The results of the completed phase I clinical trial showed that at clinically relevant dose levels, heart rate decrease was observed on the first two days of single and multiple dosing. This effect on heart rate was observed in other S1P1 modulators. Given that this is due to the mechanism of action of the drug, the AE of heart rate decrease (bradycardia) in this study is defined as a heart rate of <50 beats per minute in the awake state or a heart rate of ≥50 beats per minute in the awake state whereas subjects experience clinical symptoms due to a reduced heart rate (if subjects have a heart rate <50 beats per minute in the awake state and need clinical treatment, such condition is considered a grade II AE). In the completed Australian Phase I clinical study, it was defined that a heart rate of <45 beats per minute in the awake state was required to be reported as an AE, and this adverse event does not serve as a criterion for termination of the trial/treatment.

Reduction of peripheral blood lymphocyte count

The results of the completed Australian Phase I clinical trial indicate that at clinically relevant dose levels, the drug may reduce the peripheral blood lymphocyte count, which is the efficacy indicator of the drug. It itself is not to be reported as an AE. However, clinical diagnosis related to a decreased lymphocyte count in peripheral blood indicates AE reporting (if no diagnosis is available, it is required to report related clinical symptoms or signs).

Reduction of peripheral blood lymphocyte count

A reduction in the peripheral blood lymphocyte count directly leads to a reduction in the WBC count.

Note: In this study, heart rate decrease (bradycardia), a reduction in the peripheral blood lymphocyte count and a reduction in the peripheral WBC count (a reduction in the peripheral blood lymphocyte count directly leads to a reduction in the WBC count) are not considered as criteria for termination of the trial/treatment.

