15.1.1.1. Severity

Severity is classed per CTCAE grade. If a subject report a TEAE more than once within that SOC/PT, the AE with the worst-case severity will be used in the corresponding severity summaries.

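### Protocol 8.1.1 and 8.6 assign grade II, with no upper limit, to treated bradycardia below 50 bpm, while 8.1.2 grades every adverse event on the full CTCAE scale; nothing says which rule prevails

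*Protocol*

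**What the plan says.** Protocol 8.1.1 defines bradycardia as an adverse event in two ways: an awake heart rate below 50 bpm, or "a heart rate of ≥50 beats per minute in the awake state whereas subjects experience clinical symptoms due to a reduced heart rate". A parenthesis then fixes a grade for part of the first limb. For subjects whose awake rate is below 50 bpm it goes on: "and need clinical treatment, such condition is considered a grade II AE". Section 8.6 carries the same parenthesis ("need clinical treatment, such condition is considered a grade II AE"), so this is not a single slip.

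Protocol 8.1.2 gives the general rule: "All AEs in the trial will be graded according to the Common Terminology Criteria for Adverse Events (CTCAE), version 5.0". In its summary of the scale, grade 2 is for minimal, local, non-invasive intervention. Grade 3 includes events that lead to a hospital stay or lengthen one. The next level reads "Grade 4: a life-threatening consequence; indicating emergency treatment". Bradycardia is not excepted.

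Protocol 7.5 lists what may be given for bradycardia: atropine, then a dopamine or epinephrine drip, and finally "Performance Transcutaneous pacing can also be considered".

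SAP 15.1.1.1 takes severity from the recorded grade: "Severity is classed per CTCAE grade". SAP 4.2 plans a table of TEAEs of grade 3 or higher and a table by maximum CTCAE grade. The SAP does not mention the bradycardia parenthesis.

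**The concern.** Severity of TEAEs under CTCAE 5.0 is part of a secondary endpoint (Protocol section 4). Bradycardia with conduction abnormality is the first event of special interest in 7.5 and 8.3, and 7.5 calls a reduced heart rate an expected reaction to this drug class. It is therefore the event for which consistent severity grading matters most.

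An investigator with a treated case has two instructions. The event-specific one gives grade II whatever the treatment was. The general one lets the grade rise with hospitalisation or threat to life. Following the specific instruction over the general one would be reasonable. Two things are then at stake: the severity tables could under-report treated bradycardia, and the same event could be graded differently at different sites. Because a lower heart rate is an expected drug effect, any under-grading would be likely to fall mainly on the active arm.

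**Working it through.** The plan gives no figure to reproduce, so the check applies each rule to each kind of case.

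1. **Awake rate below 50 bpm, not treated.** The parenthesis does not apply. Only 8.1.2 governs, so there is no conflict.
2. **Awake rate 50 bpm or above, symptomatic, treated or not.** The parenthesis is limited to rates below 50, so only 8.1.2 governs. No conflict.
3. **Awake rate below 50 bpm, minor treatment, no hospital stay.** The parenthesis gives grade II. The grade 2 description in 8.1.2 can give the same. No practical conflict.
4. **Awake rate below 50 bpm, treated, leading to or prolonging hospitalisation.** The parenthesis gives grade II; 8.1.2 gives grade 3. Conflict.
5. **Awake rate below 50 bpm, life-threatening, emergency treatment such as a vasoactive drip or pacing.** The parenthesis gives grade II; 8.1.2 gives grade 4. Conflict.

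Cases 4 and 5 are foreseeable, because 7.5 itself names the drip and the pacing. Neither treatment fits the description of grade 2 in 8.1.2.

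**Effect on the tables.** Under the parenthesis, cases 4 and 5 are missing from the grade 3 or higher table and stand at grade 2 in the maximum-grade table. Under 8.1.2 they appear at grade 3 or 4. The SAP rule of using the worst grade when an event recurs in a subject does not help if every record was entered as grade 2.

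**What other outputs show.**
- A hospitalised or life-threatening event is serious under 8.2.1 and enters the serious TEAE table whatever its grade.
- An event flagged as of special interest enters that table. The table is by SOC and PT, not by grade (SAP 15.1.5), and the bradycardia threshold named in 8.3 is 45 bpm or lower. A treated event at 46 to 49 bpm might not be flagged.
- Hospitalisation required by study procedures does not count as serious (8.2.1), and subjects are recommended to stay at the centre from the day before baseline until day 2 (Table 2, note 1). A first-dose event treated during that stay would be serious only if the stay were prolonged or another seriousness criterion were met.
- Section 8.6 says bradycardia is not a criterion for ending treatment, so the table of events leading to withdrawal may not show it.

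**Scale.** With about 52 subjects planned on 0.2 mg, moving one subject into or out of the grade 3 or higher count changes the arm's rate by 1/52 = 0.019, or 1.9 percentage points. This shows the size of one event. It does not estimate how many there are.

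**The case against.** The strongest reply is that the parenthesis may only be meant to separate treated from merely observed bradycardia. Grade 1 in 8.1.2 is for events needing no intervention, so treatment would lift the event to at least grade 2 and 8.1.2 would take over from there. That reading is coherent and compatible with the general rule. It stands as a possibility, but neither section says it, and a site cannot be expected to supply it.

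A reader might infer more than the documents support:

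- **That every treated bradycardia is held at grade II.** The rule does not reach the symptomatic limb at 50 bpm or above.
- **That such events are certain to be missing from the grade 3 or higher table, so that its rate for them is zero whatever happens.** Section 8.1.2 covers all adverse events and the SAP uses the CTCAE grade. The result depends on which rule a site applied.
- **That an event like the phase I cardiac arrest (9 seconds, at 2.5 mg) would be hidden.** The parenthesis concerns heart rate decrease. An arrest or atrioventricular block recorded under its own term is graded under 8.1.2.
- **That serious bradycardia would go unseen.** The serious and special-interest tables, the summaries of concomitant medications and procedures, and the vital-sign table (heart rate 50 bpm or lower with a fall of at least 15) do not depend on grade. The loss is confined to the severity-graded tables, though the gaps noted above mean the other outputs compensate only in part.

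**Conclusion.** The contradiction is real and appears in two sections. For treated bradycardia below 50 bpm that is hospitalised or life-threatening, 8.1.1 and 8.6 read literally give grade II, 8.1.2 gives grade 3 or 4, and no text ranks them. The consequence is possible under-grading in the grade 3 or higher and maximum-grade tables, and possible inconsistency between sites. Neither is certain.

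The size cannot be stated. The documents give no rate of treated bradycardia and no indication of which rule sites used. Any effect on results requires that such events occurred and that at least one site followed the literal reading. If so, each affected subject is worth about 1.9 percentage points in a 52-subject arm, which is noticeable in a small trial. The point deserves correction because the remedy is cheap and the event is the drug class's leading cardiac risk.

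**What to change.** 1. **Protocol, or a grading note to sites.** Reconcile 8.1.1 and 8.6 with 8.1.2 so that treated bradycardia is graded on the same CTCAE 5.0 scale as all other adverse events. One way is to state grade II as a minimum rather than a fixed grade.
2. **SAP.** Add a sentence to 15.1.1.1 saying which grade feeds the grade 3 or higher and maximum-grade tables for these events.
3. **Data.** Before database lock, query the grade of every bradycardia record for which treatment was given. SAP version 1.1 is dated 18 January 2023, after the study's planned end in September 2022, so lock may already have passed. In that case, add a listing of these records with the recorded grade and the treatment given.

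The cost is a sentence in each of two protocol sections (or one note), one SAP sentence, and a short query or listing. The grade 3 or higher count may become slightly less favourable. No reporting threshold and no clinical management changes.
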